Second, the project aims to evaluate the histological composition of an incisional tissue biopsy at 6 weeks post-operative healing in patients who undergo these procedures with

Version 2 - PROTOCOL # 0145-23-FB Page 6 of 27

Institutional Review Board (IRB)

either Mucograft Seal or Colla-Plug, which will provide valuable information on the tissue response to these biomaterials at an early stage of the healing process. By addressing these information gaps, the project aims to contribute to the development of more effective socket preservation techniques and biomaterials, which will benefit patients undergoing these procedures.

CHARACTERISTICS OF THE SUBJECT POPULATION

4. Accrual

A. Is this study conducted solely at sites under the oversight of the UNMC IRB (e.g. UNMC, Nebraska Medicine, CHMC, UNO)?

Yes

1. How many subjects will need to be consented (per group, as applicable) in order to achieve the scientific objectives of the research?

24 subjects will be enrolled - 12 in each group to account for a 10% drop out rate.

2. What is the statistical or other justification for the total number of subjects described above?

A sample size of 11 in each group provides 80% power to be able to detect an absolute difference in 20 percentage-points of converted mucosa between the collagen (i.e. 50%) and mucograft (i.e. 70%) groups at four weeks, assuming a standard deviation of 15 for percentage converted mucosa and an alpha level of 0.05, using a Wilcoxon Rank Sum test.

3. How long do you estimate it will take to accrue the required number of subjects?

9 months

5. Gender of the Subjects

A. Are there any enrollment restrictions based on gender?

No

6. Age Range of Subjects

A. Will adults be enrolled ?

Yes

1. What is the age range of the adult subjects?

19-75

2. What is the rationale for selecting this age range?

Version 2 - PROTOCOL # 0145-23-FB Page 7 of 27

Institutional Review Board (IRB)

IRB PROTOCOL # 0145-23-FB Page 8 of 27

This treatment is rarely performed in children below the age of 19 and after the age of 75, adult subjects will typically show decreased wound healing due to age which could conflate findings.

B. Will children (18 years of age or younger) be included in this research?

No

1. What is the justification for excluding children from participating in this research?

♦ Research is irrelevant to children (e.g. disease or condition rarely encountered in children).

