The percentage of converted mucosa will be documented at six weeks after an extraction, and differences in the width of keratinized tissue between the collagen and mucograft groups will be assessed using a Wilcoxon Rank Sum test. As a secondary analysis, we may also look at other related demographic (e.g. sex, age, etc.) and clinical (e.g. bone width, soft tissue volume, cytokine levels, etc.) characteristics to see if they have associations with the percent keratinized gingiva, using Spearman correlations for continuous variables, or Wilcoxon Rank Sum/Kruskal Wallis tests for categorical variables.

C. Select any of the following that apply to the research:

Phase I study

♦ Randomization

Placebo (or non-treatment arm)

Washout

Sensitive surveys or questionnaires

None of the above

Option chosen: Randomization

Describe randomization process and schedule

A statistician will generate a randomization schedule, after which someone not involved in the treatment of these patients will put each randomized treatment assignment into separate

envelopes, which will be given to the clinical provider close to the time the material will be placed, after the patient has been enrolled/consented into the study.

Version 2 - PROTOCOL # 0145-23-FB Page 12 of 27

Institutional Review Board (IRB)

IRB PROTOCOL # 0145-23-FB Page 13 of 27

D. Identify:

1. All procedures, interventions, evaluations and tests performed solely for research purposes (eg, administration of an investigational drug or a new psychological assessment instrument; randomization)

Procedures performed solely for research purposes include: the collection of gingival crevicular fluid (GCF); soft tissue biopsy at 6-weeks post-procedure.

2. All procedures, interventions, evaluations and tests performed for clinical indication but more frequently than they would be if the subject was not participating in the research (eg, extra blood tests; additional radiology exams)

It is not typical to have an intraoral scan done at post-operative visits. However, this takes less than 2 minutes to perform and has no contraindications or risks. It is simply a data collection process for dentists to measure changes in our patients over time.

E. Describe briefly the statistical methods used to analyze the data (or reference the appropriate section of the detailed protocol or grant).

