are grafted for future implant placement. The study will include nonsmoking adults aged 18-75 requiring premolar or anterior tooth extraction and graft procedures, who are in good general health and willing to provide informed consent. Exclusion criteria include a history of radiation therapy or bisphosphonate use, pregnancy or breastfeeding, systemic conditions that affect bone healing, contraindications to dental implants, and inability to attend follow-up visits. The study will be a double-blind randomized controlled trial involving 24 patients who will be assigned to two groups. Prior to tooth extraction, baseline data will be collected; including gingival crevicular fluid (GCF) sampling, and a limited field Cone Beam Computed Tomography (CBCT) radiograph. A reference digital scan will be taken to measure volumetric changes in soft tissue. Routine, atraumatic extraction of the tooth under local anesthetic will be performed. Following extraction, hydrated AllOss 50/50 DFDBA:DFDBA bone particulate will be condensed following a routine protocol. One group will receive Mucograft Seal over the graft, and the other group will receive Integra HeliPlug. Patients will be seen at a standard 2-week follow up to remove sutures, have a GCF sampling at the adjacent teeth and take another digital scan. Patients will be seen for an additional 6-week follow up to take a small (2mm) incisional biopsy for histological analysis. Another digital scan and GCF sampling will be taken. Final evaluation will be 3 months post-extraction and will include a localized CBCT evaluation for implant planning and another measure of soft tissue changes with a digital scan. At the time of implant surgery, the core of bone removed during osteotomy will be histologically analyzed for percentage of vital bone. Adverse events will also be recorded at each visit. The primary outcome measure will be the histological composition of tissue at 6 weeks and volumetric tissue changes. The secondary outcome measures will be adverse events, bone density on the post-operative CBCT and percentage of vital bone at implant placement.

PURPOSE OF THE STUDY AND BACKGROUND

2. Purpose of the Study

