What are the specific scientific objectives of the research? The primary objectives of this study are to compare the efficacy of a porcine collagen Version 2 - PROTOCOL # 0145-23-FB Page 5 of 27 Institutional Review Board (IRB) IRB PROTOCOL # 0145-23-FB Page 6 of 27 membrane to a bovine collagen wound dressing for atraumatic extractions, in terms of their ability to act as a barrier and containment material over atraumatic extraction sites that are grafted for future implant placement. This will be measured by volumetric and linear dimensional changes in the soft tissue and the histological composition of keratinized tissue after healing.

The secondary objectives of the study are to evaluate the radiographic bone density and percentage vital bone at implant planning and placement.

3. Background and Rationale

Describe the background of the study. Include a critical evaluation of existing knowledge, and specifically identify the information gaps that the project is intended to fill.

Extraction and graft procedures are commonly performed in dental clinics where future implant placement is desired due to the large soft and hard tissue dimensional changes that occur as a socket heals (Araujo 2005, Chappuis 2017). While there are several techniques for ridge preservation, it is generally accepted that minimizing trauma from the extraction and

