flap reflection greatly decreases loss of hard and soft tissue (Fickl 2008). This is why a popular method is some form of Bio-Col technique where a bone graft is condensed into the socket and then a collagen wound dressing, or plug, is used to prevent wash out of the graft. (Sclar 1999, Kotsakis 2014). While cost effective, and easy to place without flap reflection, a collagen plug can be dislodged quickly and has been shown to have a large soft tissue loss during healing (Morelli 2020, Thoma 2018). Therefore, other soft tissue alternatives have been investigated as an alternative membrane (Ghanaati 2017) Several studies have investigated the efficacy of Mucograft Seal as a barrier membrane to promote bone regeneration in socket preservation techniques. (Jung 2013) Mucograft Seal is a porcine collagen membrane that is shaped ideally for easy coverage of a socket. Because it is a pure matrix of Type I and Type III collagen, it is able to stay more dimensionally stable, making it an ideal material to combat soft tissue reduction as a site heals. It is currently used as a replacement for free gingival grafting coverage, such as with the soft tissue punch technique (Jung 2004), but has not been compared to a collagen wound dressing for critical early healing characteristics such as inflammatory cytokines. Additionally, there is limited information on the specific histological composition at 6 weeks post-operative healing in patients who undergo socket preservation with Mucograft Seal or Colla-Plug.

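### Volumetric soft-tissue change is named as part of the primary outcome, but the written between-material test and the sample size address only the histology half

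*Protocol*

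**What the plan says.** The Protocol gives volumetric change a status in several places.

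- **Section II, item 1 (abstract), primary outcome:** "The primary outcome measure will be the histological composition of tissue at 6 weeks and volumetric tissue changes".
- **Same item, secondary outcomes:** "The secondary outcome measures will be adverse events, bone density on the post-operative CBCT and percentage of vital bone at implant placement". Volume is not among them.
- **Item 2 (Purpose of the Study):** the primary objective is to compare the two materials, and "This will be measured by volumetric and linear dimensional changes in the soft tissue and the histological composition of keratinized tissue after healing".
- **Item 2, secondary objectives:** "The secondary objectives of the study are to evaluate the radiographic bone density and percentage vital bone at implant planning and placement". Volume is again absent.
- **Item 3 (Background and Rationale):** the porcine membrane is described as dimensionally stable, "making it an ideal material to combat soft tissue reduction as a site heals".
- **Item 12.B (Statistical Analysis), repeated in 12.E, the one between-material test:** "differences in the width of keratinized tissue between the collagen and mucograft groups will be assessed using a Wilcoxon Rank Sum test".
- **Same paragraph, the only mention of volume:** "As a secondary analysis, we may also look at other related demographic (e.g. sex, age, etc.) and clinical (e.g. bone width, soft tissue volume" and cytokine levels, to be examined for association with percent keratinized gingiva.
- **Item 4.A.2 (sample size):** a 20-point difference "between the collagen (i.e. 50%) and mucograft (i.e. 70%) groups at four weeks, assuming a standard deviation of 15 for percentage converted mucosa".

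**The concern.** The primary label on volume does not look like a slip. It appears in both the abstract and the objectives, both secondary lists leave volume out, and resisting soft-tissue loss is the reason given for studying the membrane. The statistical section treats volume differently: optional, labelled secondary, and a possible correlate of the histology result. Correlating volume with keratinized gingiva does not tell the reader whether the two materials differ in volume change.

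Two things are at stake. First, the 80% power statement reads as if it supported the primary outcome, when it supports one of its two parts. Second, item 12.B schedules intraoral scans at baseline, 2 weeks, 6 weeks and 3 months, and no visit is named for the volumetric outcome. If a between-arm comparison is added later, the visit (any of three) and its weight against histology could be chosen after data are seen.

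**Working it through.** **Step 1. Status of each variable, side by side.**

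| Place in Protocol | Histology | Soft-tissue volume |
|---|---|---|
| Item 1, primary outcome | named | named |
| Item 1, secondary outcomes | not listed | not listed |
| Item 2, primary objective | named | named, with linear change |
| Item 2, secondary objectives | not listed | not listed |
| Item 4.A.2, sample size | percentage converted mucosa | no input |
| Items 12.B and 12.E, between-material test | width of keratinized tissue, Wilcoxon rank sum | none written |
| Items 12.B and 12.E, optional secondary analysis | the variable being explained | one of several possible correlates |

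The first four rows treat the two outcomes alike; the last three do not. That is the conflict.

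**Step 2. Reproduce the plan's own figure.** Inputs from item 4.A.2: 50% versus 70%, SD 15, alpha 0.05, 80% power, Wilcoxon rank sum, 11 per group. Sidedness is not stated; two-sided is assumed.

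- Standardized difference: d = 20 / 15 = 1.333.
- Normal approximation: n = 2 × (1.96 + 0.84)² / 1.333² = 8.8, so 9 per arm.
- Noncentral t: n = 9.89 per arm. Allowing for the Wilcoxon test's efficiency under normality, 9.89 × π/3 = 10.36, so 11 per arm.
- Simulated exact Wilcoxon test on normal data (40,000 trials): power 76.2% at 10 per arm and 81.7% at 11 per arm. At 11 per arm the exact test rejects when the smaller U is 30 or less; its actual size is 0.0473.
- A one-sided normal approximation gives 7 per arm and does not match, which supports the two-sided reading.

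The stated 11 per group is sound for converted mucosa.

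**Step 3. What 11 per arm means for volume.** The Protocol gives no volumetric difference, SD or visit, so no power can be derived from it. For illustration only, over an assumed range of true differences in SD units, the same two-sided exact test at 11 per arm gives:

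| Assumed volume difference | Power |
|---|---|
| 0.5 SD | about 19% |
| 0.8 SD | about 40% |
| 1.0 SD | about 57% |
| 1.2 SD | about 74% |
| 1.33 SD | about 82% |

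Volume would have about 80% power only if the materials differed by roughly 1.3 SD, close to the standardized effect assumed for histology. Nothing in the Protocol says whether that is plausible.

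**Step 4. Related alignment points.** These are not the basis of the finding, but they sit in the same sentences. The trial is sized on a percentage, while the written test is on a width. The sample size refers to four weeks and item 16 (Potential Risks) places soft-tissue sampling at 4 weeks, while the abstract and item 12 place the biopsy at 6 weeks.

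**The case against.** The statistical text answers a form item that asks for a brief description, and an analysis plan may exist that is not shown. The test, estimate, interval and visit for volume are details a protocol often leaves to that plan. A variable can be a primary outcome and also serve as an exploratory correlate, so the secondary-analysis sentence does not by itself remove volume from the primary outcome. The study has 24 patients, the scans are planned in both arms, and wording can repair the problem without loss of data.

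Much of this stands. The absence of volumetric test details is not, taken alone, an error. What remains is that the Protocol assigns a primary status in two places, then writes a statistical section and a power statement that cover only half of it. An analysis plan cannot decide which outcomes the Protocol calls primary, and the stated power is a Protocol statement.

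Three stronger readings are tempting but unsupported:

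- **That the trial will make no volumetric comparison.** The objective in item 2 does promise one; only the method is unwritten.
- **That the visit and weight will be picked after the data are seen.** This is a risk. An analysis plan or the registry entry may already fix them.
- **That the false-positive rate is inflated, or that power for a two-part success criterion is too low.** Both need a success rule the Protocol does not state, and the second also needs a volume effect it does not give.

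**Conclusion.** The finding holds as an internal inconsistency over primary status. One of two named primary outcomes has no between-material test in the statistical section and no place in the sample size, so the 80% power (82% on recalculation) belongs to converted mucosa only. The size of the problem for volume cannot be computed from the Protocol; the 57% at 1.0 SD is an illustration resting on an assumed effect, normal data and a two-sided test at 0.05. This should be fixed, but it does not undermine the design: data capture is unaffected, and the histology sample size is correct on its stated inputs.

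**What to change.** Before any outcome data are examined, give volume one status and use it in the abstract, the objectives and the statistical section. If outcome data have already been seen, demoting a named primary outcome would itself be a change of outcome and would have to be reported as such.

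- **Cheapest option.** Make 6-week histology the single primary outcome, to which the 80% power applies. Name change from the baseline scan in soft-tissue volume as a secondary outcome, compared between arms by Wilcoxon rank sum with an estimate and 95% CI at one pre-named visit. Treat linear dimensions as supportive. The correlation with keratinized gingiva can stay as exploratory.
- **If volume stays co-primary.** Name the single volumetric variable and its visit, and state the success rule: both must succeed, or alpha is split. Say that the 80% power applies to histology alone at 0.05. For scale, an assumed even split at 0.025 each lowers histology power at 11 per arm from about 82% to about 72%.
- **In the same edit.** Make the tested histology variable the percentage of converted mucosa used for the sample size, and say how it is derived from the measured width. Reconcile the four-week references in items 4.A.2 and 16 with the 6-week biopsy.

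The first option costs wording only, plus the registry entry if it repeats the same text. It adds no visits, scans or subjects. Its downside is that the volumetric result, which the rationale stresses, carries less weight as a secondary outcome.

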
to the research: Phase I study ♦ Randomization Placebo (or non-treatment arm) Washout Sensitive surveys or questionnaires None of the above Option chosen: Randomization Describe randomization process and schedule A statistician will generate a randomization schedule, after which someone not involved in the treatment of these patients will put each randomized treatment assignment into separate envelopes, which will be given to the clinical provider close to the time the material will be placed, after the patient has been enrolled/consented into the study. Version 2 - PROTOCOL # 0145-23-FB Page 12 of 27 Institutional Review Board (IRB) IRB PROTOCOL # 0145-23-FB Page 13 of 27 D. Identify: 1. All procedures, interventions, evaluations and tests performed solely for research purposes (eg, administration of an investigational drug or a new psychological assessment instrument; randomization) Procedures performed solely for research purposes include: the collection of gingival crevicular fluid (GCF); soft tissue biopsy at 6-weeks post-procedure. 2. All procedures, interventions, evaluations and tests performed for clinical indication but more frequently than they would be if the subject was not participating in the research (eg, extra blood tests; additional radiology exams) It is not typical to have an intraoral scan done at post-operative visits. However, this takes less than 2 minutes to perform and has no contraindications or risks. It is simply a data collection process for dentists to measure changes in our patients over time. E. Describe briefly the statistical methods used to analyze the data (or reference the appropriate section of the detailed protocol or grant). The percentage of converted mucosa will be documented at six weeks after an extraction, and differences in the width of keratinized tissue between the collagen and mucograft groups will be assessed using a Wilcoxon Rank Sum test. As a secondary analysis, we may also look at other related demographic (e.g. sex, age, etc.) and clinical (e.g. bone width, soft tissue volume, cytokine levels, etc.) characteristics to see if they have associations with the percent keratinized gingiva, using Spearman correlations for continuous variables, or Wilcoxon Rank Sum/Kruskal Wallis tests for categorical variables. F. Does this study involve the collection of blood, urine, saliva or other human biological material (HBM)? Yes 1. Does this research involve genetic testing including Genome Wide Association Studies (GWAS), Whole Genome Sequencing (WGS) or Whole Exome Sequencing (WES)? No G. Does this study involve the creation of a tissue bank for future unspecified research? This includes un-used (excess) blood, urine, or tissue, obtained for clinical indication or for research, or additional human biological material collected specifically for future research. No DRUGS, BIOLOGIC DRUGS AND DEVICES Version 2 - PROTOCOL # 0145-23-FB Page 13 of 27 Institutional Review Board (IRB) IRB PROTOCOL # 0145-23-FB Page 14 of 27 13. Drugs and Biologic Drugs 1. Does this research involve the use of drugs or biologics? Yes A. Are any of the drugs or biologics used in this research not FDA-approved? No B. Are any of the drugs used in this study FDA Approved? Yes 1. Will data obtained from this research study be used to support a new indication, new labeling or a change in advertising of an FDA-approved drug or biologic? No 2. Will the use of an

FDA-approved drug in this research study involve a route of administration, dosage level or patient population that significantly increases the risks (or decreases the acceptability of the risks) associated with the use of the drug product? No C. Do any of the sponsors of this research require compliance with ICH-GCP? No 14. Devices 1. Does this research involve a medical device(s) (including an in vitro device [IVD] (assay), and medical software)? No

CONFIDENTIALITY AND PRIVACY 15. Confidentiality and Privacy A. Describe where research data will be stored. Check all that apply. [contact] (secure UNMC or UNO designated cloud-based storage site) Microsoft Office 365 application (including SharePoint, OneDrive for Business, Teams or Streams) (UNMC, UNO or NU system instance) (secure UNMC or UNO designated cloudbased storage site) Other secure UNMC or UNO designated cloud-based storage site - describe: OnCor Clinical Trial Management System (secure server at UNMC, CHMC, Nebraska Medicine, and/or UNO) Version 2 - PROTOCOL # 0145-23-FB Page 14 of 27 Institutional Review Board (IRB) IRB PROTOCOL # 0145-23-FB Page 15 of 27 CCORDA database (biostatistics) (secure server at UNMC, CHMC, Nebraska Medicine, and/or UNO) RITO-hosted databases (for example, REDCap, CV-QOR, Onchem Trials, XNAT) (secure server at UNMC, CHMC, Nebraska Medicine, and/or UNO) Nebraska Medicine PACS (for image files) (secure server at UNMC, CHMC, Nebraska Medicine, and/or UNO) Other secure server at UNMC, CHMC, Nebraska Medicine, and/or UNO - describe: On an NSRI or designated high security .gov storage site On a VA-approved storage vehicle for a VA-approved study On a remote secure server and/or database maintained by the sponsor accessible through the internet On a secure server and/or database hosted and maintained by another institution accessible through the internet On a device or mobile application provided by the sponsor to upload data to a coordinating center or central database On a device or mobile application being developed by a sponsor or by a UNMC, CHMC or UNO investigator On a device or mobile application that connects to the internet through UNMC or NM network (wired or wireless) On an encrypted, password protected portable computer, or flash drive Other - describe: ♦ In hard copy (other than signed Consent Forms) Option chosen: In hard copy (other than signed Consent Forms) a. Please provide justification for use of hard copies Data collection is easiest and most secure in our department when done with hard copies. The room is secured by key card access and data will be stored in locked cabinets. Only authorized personnel will be able to access them. Option chosen: In hard copy (other than signed Consent Forms) b. Will hard copies will be transported from one site to another, on or off campus? No B. Will any of the following subject identifiers be recorded (at any time) in association with the research data? Yes 1) Indicate the subject identifiers that will be recorded. Check all that apply. Name ♦ Version 2 - PROTOCOL # 0145-23-FB Page 15 of 27 Institutional Review Board (IRB) IRB PROTOCOL # 0145-23-FB Page 16 of 27 DATES (e.g. date of study visit, date of sample collection, birth, admission, discharge) Postal address information: street address, city, county, precinct, ZIP code Telephone numbers Fax

numbers Electronic mail addresses Social Security numbers ♦ Medical Record numbers Health plan beneficiary numbers Account numbers Certificate/license numbers Vehicle identifiers and serial numbers, including license plate numbers Device identifiers and serial numbers Web Universal Resource Locators (URLs) Internet Protocol (IP) address numbers Biometric identifiers, including finger and voice print Full face photographic images [and any comparable images] No Identifier 2) Will a unique subject identifying number (e.g., S1, S2, S3), characteristic or code be used to link data to any of the identifiers listed above? Yes a. Where will the key (that links the unique subject identification code to the subject's name or other identifier) be stored? The key will be stored in a locked filing cabinet within a locked room in the Cruzan Center for Dental Research. The unique identifier that will be used to code the data is as follows: each subject will be given a number (i.e. N1, N2...N25). The specific appointment visit (baseline, 2 weeks, 3 months) data will be coded as follows: N1-0 (baseline), N1-2 (two weeks), N1-3 (3 months). b. Does the code number include the subject's initials or other subject identifier as part of the code? No 3) What is the justification for recording the specific subject identifiers listed above? Check all that apply. ♦ Schedule appointments Collect continuous clinical information from the medical records ♦ Follow-up with subjects Link stored tissue with subject identification for it to be withdrawn in the future if requested Version 2 - PROTOCOL # 0145-23-FB Page 16 of 27 Institutional Review Board (IRB) IRB PROTOCOL # 0145-23-FB Page 17 of 27 Compensation Other. Explain. 4) How long will the subject identifiers be maintained in association with the research data? Subject identifiers will be maintained until data have been statistically analyzed and reports published and no less than 7 years following completion of research per Nebraska state law and NRPP policy. 5) How will all of the identifiable research data be destroyed (e.g., all identifiers stripped from the data and destroyed, hard copies shredded etc) when the identifiable data is no longer required? Subject identifiers will be stripped from the data and destroyed once it is no longer required. C. Will research data that contain subject identifiers be disclosed to: Other investigators at UNMC, NM, UNO or CHMC who are not listed in Section I of this application? No 2. Investigators outside of UNMC, NM, UNO or CHMC? No 3. Will research data that contain subject identifiers be disclosed to any commercial sponsor or contract research organization (CRO), or to any other external organization or entity (e.g., NCI cooperative groups)? No D. What provisions will be in place to protect the subject's privacy? Check all that apply. ♦ Ensuring that only personnel listed on the IRB application Section I.3(A-E) are present during the consent process. ♦ Ensuring that the fewest number of individuals possible are aware of the subject's participation in the research. ♦ Ensuring that the research activities are performed in as private of a place as possible. Other. Explain. E. Does this research involve data banking at UNMC, NM, UNO or CHMC, or by an outside organization (e.g. NCI Cooperative Group, pharmaceutical company) for future research that is not related to this study? Version 2 - PROTOCOL # 0145-23-FB Page 17 of

27 Institutional Review Board (IRB) IRB PROTOCOL # 0145-23-FB Page 18 of 27 No RISK/BENEFIT ASSESSMENT 16. Potential Risks What are the potential risks associated with each research procedure, intervention, evaluation and/or test? If data are available, estimate the probability that a given harm may occur and its potential reversibility. Potential risks associated with soft tissue sampling at 4-weeks includes minimal pain and adjacent tooth sensitivity. The soft tissue and GCF specimens will be collected in plastic-capped vials and frozen until analysis. These vials will be labeled with the subject's number and visit (N1-0, N2-2) and will not be labeled with any personal identifying information, thus breach of confidentiality is not at risk. Potential risks associated with limited view CBCT include increase exposure to radiation. This risk is inherent to any dental radiography and the limited-view CBCT pre-extraction and post-extraction is standard therapy for dental implant treatment planning. 17. Risk Classification What is the overall risk classification of the research? Minimal risk ♦ Greater than minimal risk 18. Minimization of Risk A. Describe how the subjects of the research will be monitored by the investigators and other research personnel to ensure their safety. Subjects of the research will be monitored with follow-up phone calls. If any postoperative concerns develop, they will be seen in the graduate periodontal clinic for follow-up. B. Describe how the data collected will be monitored to ensure the safety of subjects. Identify who will perform the ongoing data and safety analysis, and describe the frequency of data analysis. If there is an independent Data and Safety Monitoring Board (DSMB) provide the charter, or describe (1) the composition of the DSMB membership, (2) the frequency of DSMB meetings and reports. Data collection will be monitored by study personnel and if a decline in the subject's periodontal condition is noted, they will be referred to the graduate periodontal residency at UNMC College of Dentistry for a full evaluation. The contact information for the study investigators and personnel are on the consent form that will be sent home with each Version 2 - PROTOCOL # 0145-23-FB Page 18 of 27 Institutional Review Board (IRB) IRB PROTOCOL # 0145-23-FB Page 19 of 27 subject. C. Describe the auditing plan for research conducted. Identify who will conduct the audits and specify the audit frequency. Ten percent of the case report forms will be reviewed by the Associate Dean of Clinics, [name], at the COD semi-annually and audited against the primary dental record. Any violations or unexpected outcomes will be reported to the IRB. D. Describe the specific subject withdrawal criteria. Subjects will be withdrawn if they are non-compliant to their postoperative appointments. E. Describe the stopping rules for the research (e.g., the specific criteria for halting or early termination of the study). If 10% of subjects suffer an adverse event, such as bleeding or pain associated with the soft tissue sampling greater than that expected associated with a similar extraction without sampling, the study will be stopped. F. Describe plans and resources available to promptly address any subject injury. The investigators are board-certified periodontists or periodontal residents, so any adverse effects will be addressed with a thorough evaluation and appropriate treatment. 19. Potential Benefits to the Subject

Is there the prospect for direct benefit (eg, research on diagnosis or treatment of disease)? No 20. Potential Benefits to Society Describe the potential benefits to society that may reasonably be expected to result from this research. A potential benefit to society would be clarification and understanding of the soft tissue healing capabilities of common materials used for this procedure. **FINANCIAL OBLIGATIONS AND COMPENSATION** 22. Financial Obligations of the Subject A. Who will pay for research procedures, interventions, evaluations and tests? Check all that apply. Sponsor Grant CRC, CCTR Version 2 - PROTOCOL # 0145-23-FB Page 19 of 27 Institutional Review Board (IRB) IRB PROTOCOL # 0145-23-FB Page 20 of 27 Costs or fees waived by Nebraska Medicine, UNMC- P, CHMC or CSP ♦ Department/Section funds Other. Explain B. Will any of the research procedures, interventions, evaluations and tests described above be charged to the Subject, the Subject's health insurance, or Medicare/Medicaid? Yes 1. Provide additional detail and justification for charging as noted. The subject will be not be charged for any research procedures or interventions. The subject will be charged for non-research related procedures (extraction, bone graft, limited view CBCT). C. Are there any other financial obligations that the subject will incur as a result of participating in the study? No 23. Compensation to the Subject for Participation A. Will the subject receive any compensation for participation? No PRIOR REVIEW 24. Prior IRB Review A. Has this study (or one substantially similar) been previously submitted to the UNMC IRB (or the Joint Pediatric IRB) and then withdrawn by the investigator for any reason? No B. To the best of your knowledge, has this study (or one substantially similar) been considered by another IRB and disapproved? No SUBJECT IDENTIFICATION & RECRUITMENT 25. Method of Subject Identification and Recruitment A. Will prospective subjects learn about the research and then contact the investigator about participation (for example, in response to a print, electronic, radio or television advertisement; referral by a clinician or other specifically for this research)? Version 2 - PROTOCOL # 0145-23-FB Page 20 of 27 Institutional Review Board (IRB) IRB PROTOCOL # 0145-23-FB Page 21 of 27 No B. Will the investigator make the initial contact with the potential subject to tell him/her about the research (for example, by contacting existing or past previous patients or research participants; or by contacting prospective subjects thru school records, or thru support groups or other Interest Groups; or thru use of the Hospital Opt-In Database)? Yes 1. How will prospective subjects be identified? Patients that meet the study criteria will be identified in the UNMC COD clinic during normal clinical treatment. 2. Will potential subjects be screened for eligibility prior to informed consent? No 3. How will potential subjects be approached and invited to participate? Eligible patients will be asked if they want to participate in the study. a. Describe the process of initial contact Patients that would otherwise be presenting to the clinic for extraction and grafting will be invited to participate in the study. b. Who will make the initial contact? One of the investigators or collaborators. c. Does that person have ethical access to information about potential

subjects? Yes i. Describe All investigators and collaborators are responsible for supervising dental students in patient care in the clinic where potential subjects are treated, therefore direct contact with potential subjects and their records is part of that supervision. C. Will this study be listed in the clinical trial registry at www.clinicaltrials.gov? Yes 1. Provide the NCT#. NCT application has been submitted, awaiting NCT#. Will inform the IRB when it comes Version 2 - PROTOCOL # 0145-23-FB Page 21 of 27 Institutional Review Board (IRB) IRB PROTOCOL # 0145-23-FB Page 22 of 27 through. 2. Identify who holds the NCT# ♦ PI Sponsor OBTAINMENT OF INFORMED CONSENT 26. Waiver or Alteration of Informed Consent A. Is a complete waiver or alteration of consent requested? No 27. Waiver of Signed Consent Is a waiver to obtain signed consent requested? No 29. Process of Informed Consent A. When will the prospective subject/parent(s)/guardian(s)/LAR be approached relative to their/the subject's actual participation in the study? Prospective subjects will be approached after it has been determined that they have a nonrestorable anterior or premolar tooth that needs extraction and they have expressed interest in replacing the tooth with a dental implant. Subjects will be referred to the graduate periodontal clinic where they will be approached by study personnel (periodontal resident) about their interest in participating in the study. B. Where will informed consent be obtained, and how will the environment be conducive to discussion and thoughtful consideration? Informed consent will be obtained in a private room in the Cruzan Center for Dental Research. C. Who will be involved in the process of consent and what are their responsibilities? The investigators will explain the research, ask questions to be certain that the subject understands the procedure, and answer any subject questions.

Additionally, investigators will also ask questions to ensure that subjects understand their rights as research subject D. Is there any limitation on the amount of time allotted to the process of consent? No E. How will the process of consent be structured for subjects who are likely to be more Version 2 - PROTOCOL # 0145-23-FB Page 22 of 27 Institutional Review Board (IRB) IRB PROTOCOL # 0145-23-FB Page 23 of 27 vulnerable to coercion or undue influence? All subjects approached about this study will already have made the decision to extract the tooth and have expressed interest in implant replacement of that tooth.

Additionally, they will already have been counseled on the process of extraction, grafting and implant placement; including the costs and time required for successful treatment. Investigators acknowledge concerns regarding the potential subject misinterpreting the study as standard of care, or having his/her decision regarding participation influenced by concerns about disappointing or offending his/her care provider by having the introductory and informed consent conversations completed by study personnel who are not familiar to the subject. The subject will not have had previous contact with study personnel, thus minimizing the concern about disappointing or offending his or her provider. Additionally, extreme care will be taken during discussion/description of the study with the subject to highlight that the removal of soft tissue is not standard of care for routine extraction and

